7.5 Causality Assessment of Adverse Events

For all AEs, the Principal Investigator will provide an assessment of causal relationship to the study treatment (active or placebo). The causality assessment must be recorded in the subject's source documents and on the AE CRF. Causal relationship will be classified according to the following criteria:

1. *Unrelated*: The event is clearly due to causes other than the active study drug.
2. *Unlikely*: The event is doubtfully related to active study drug. The event was most likely related to other factors such as the patient's clinical state, concomitant drugs or other therapeutic interventions.
3. *Possible*: The event follows a reasonable temporal sequence from the time of active study drug administration, but could have been produced by other factors such as the patient's clinical state, therapeutic interventions or concomitant drugs.
4. *Probable*: The event follows a reasonable temporal sequence from the time of active study drug administration, and follows a known response pattern to the drug. The toxicity cannot be reasonably explained by other factors such as the patient's clinical state, therapeutic interventions or concomitant drugs.
5. *Definite*: The event follows a reasonable temporal sequence from the time of active study drug administration, follows a known response pattern to the drug, cannot be reasonably explained by other factors such as the patient's condition, concomitant drugs or therapeutic interventions, AND either occurs immediately following active study drug administration, improves on stopping the study drug, or reappears on re-exposure.

7.5.1 Potential Adverse Events Associated with ORMD-0801

Hypoglycemia and associated symptoms (e.g., weakness, dizziness, shakiness, increased sweating, palpitations, or confusion), have been associated with insulin administration, including ORMD-0801. Animal reproductive studies have not been conducted with ORMD-0801. It is not known whether ORMD-0801 can cause fetal harm when administered to a pregnant woman. It is also not known whether this product is excreted in human milk. Pregnant or breastfeeding women are excluded from this study.

Long-term animal studies have not been completed to assess whether ORMD-0801 impairs fertility.

7.6 Adverse Event Severity Assessment

The severity of each AE will be graded according to the NCI CTCAE, version 4.03. The severity of AEs that are not specifically listed in the CTCAE will be categorized according to the general guidelines provided in the CTCAE, and as summarized in the table below.

General Guidelines for Severity Assessment of Adverse Events

Grade 1: Mild; asymptomatic or mild symptoms; clinical or diagnostic observations only; intervention not indicated.
Grade 2: Moderate; minimal, local or noninvasive intervention indicated; limiting age-appropriate instrumental activities of daily living (ADL) [preparing meals, shopping for groceries or clothes, using the telephone, managing money, etc.].
Grade 3: Severe or medically significant but not immediately life-threatening; hospitalization or prolongation of hospitalization indicated; disabling; limiting self-care ADL (bathing, dressing and undressing, feeding self, using the toilet, taking medications, and not bedridden).
Grade 4: Life-threatening consequences; urgent intervention indicated.
Grade 5: Death related to AE.

Note the distinction between the severity and the seriousness of an AE. A severe AE is not necessarily a SAE. For example, a headache may be severe (interferes significantly with patient's usual function) but would not be classified as serious unless it met one of the criteria for SAEs, listed above in Section 7.3.

7.7 Expectedness of Adverse Event

An unexpected AE is defined in 21 CFR 312.32(a) as follows:

An AE is considered “unexpected” if it is not listed in the IB or is not listed at the specificity or severity that has been observed; or, if an IB is not required or available, is not consistent with the risk information described in the general investigational plan or elsewhere in the current application, as amended.

7.8 Assessment of Adverse Event Outcome

Outcome of AEs will be defined according to ICH Topic E2B, ICH Guideline.

- **Recovered/Resolved:** The subject has recovered fully from the AE without any remaining effects or impairment.
- **Recovered/Resolved with Sequelae:** The subject has recovered, but with an after effect possibly due to disease or treatment.
- **Not Recovered/Not Resolved:** The condition is still present.

- **Fatal:** Fatal should only be used when death is possibly related to the AE.
- **Unknown:** The primary outcome is not known at the time of the final assessment. If an outcome for an AE is not available at the time of the initial report, follow-up will proceed until an outcome is known or followed up to the Final Study Visit. Any subject with a possible study treatment-related AE at the Final Study Visit will be followed until resolution or stabilization of the event. Further, any SAE, whether or not related to Study treatment (active or placebo), that occurs within 30 days following the last dose of Study treatment will be followed until resolution or stabilization of the event.

7.9 Clinical Findings

Any significant clinical findings at the Follow-Up Visit will be followed until the condition returns to pre-study status, stabilizes, or can be explained as not being study treatment related. If the clinical finding is reported as an AE (per the criteria outlined in Section 10.2), the follow-up procedures for AEs defined above will apply.

8 STATISTICAL METHODS

This section describes the statistical methods to be used for the analysis and reporting of data collected under Protocol No. ORA-D-012. Additional details will be provided in the statistical analysis plan.

8.1 Sample Size

A total of 30 subjects will be randomized to receive either placebo, ORMD-0801 460 IU qd, ORMD-0801 460 IU bid, or ORMD-0801 460 IU tid during each treatment period.

Safety will be a secondary endpoint for this trial and will be assessed primarily based on AEs. Secondary safety assessments will include physical examination, 12-lead ECG, vital signs (including weight, seated SBP/DBP, heart rate, and temperature), and clinical safety labs (hematology, serum chemistry, and urinalysis).

This study is not powered for statistical significance.

8.2 Pharmacokinetic/Pharmacodynamic Evaluation

The PK/PD analysis will be conducted using model-independent methods and will be based on plasma concentrations of insulin and C-peptide.

Individual plasma concentrations of insulin and C-peptide will be listed for each subject and sampling time and summarized descriptively using the arithmetic mean, SD, CV (%), median, minimum and maximum. Individual plasma concentration-time profiles of insulin and C-peptide will be plotted on both a linear and a semi-logarithmic scale. Mean values will also be presented graphically.

8.3 Continuous Glucose Monitor Evaluation

For the purpose of analysis:

- 24-hour will be considered to be from 6AM to 6AM,
- Daytime will be considered to be from 6AM to 10PM, and
- Nighttime will be considered to be from 10PM to 6AM.

The last 2 days with at least 80% of expected measurements prior to dosing will be considered the run-in days for each of the parameters. The last 2 days with at least 80% of expected measurements prior to 8 hours after the last dose will be considered the on treatment days. The measurements more than 8 hours after the last dose will be considered the follow-up days.

The area under the curve (AUC) will be derived for each of the time periods (24-hour, daytime and nighttime) using the indicated days (run-in days, treatment days and follow-up days). The average glucose measurement will be derived by dividing the AUC by the number of observed hours. The average change from run-in will be derived for each treatment regimen for both the treatment days and the follow-up days.

The placebo adjusted change in means will be derived for each of the active therapy regimens by subtracting the placebo mean (the mean change from run-in while the subject was receiving placebo) from the active therapy mean (the mean change from run-in while the subject was receiving the active therapy). The placebo adjusted change in means will be derived for both the treatment days and the follow-up days.

The placebo adjusted change in means will be analyzed using an Analysis of Variance (ANOVA) with treatment as the main effect to determine whether multiple doses a day has an effect on the CGM parameters.

The ratios of the placebo adjusted change in means between the active treatments within each subject will also be derived to estimate the magnitude of the dose response.

Summary statistics will be presented for both the placebo adjusted change in means and the ratios of the placebo adjusted change in means. Analysis results will be presented for the change in means.

8.4 Safety Evaluation

8.4.1 Safety Population

All randomized subjects who receive at least one dose of study treatment will be included in the safety analysis population.

8.4.2 Adverse Events

AEs will be coded using the most current version of MedDRA. The severity of AEs will be graded according to NCI CTCAE version 4.03. AEs will be regarded as “pretreatment” if they occur during the placebo washout period or placebo run-in period. TEAEs are defined as any AE that starts or increases in severity after the first randomized dose of study treatment on Visit 2/Day 4.

The incidence of TEAEs will be tabulated by MedDRA preferred term, system organ class, treatment group, severity, and assigned relationship to study treatment. The incidence for each TEAE will be provided as the total number of subjects that experienced the TEAE, as well as the percentage of the population that this represents. If a TEAE is reported more than once for a

given subject, the greatest severity and the worst-case attribution will be presented in the summary tables.

TEAEs will be listed for individual subjects, along with information regarding onset and end dates, onset time where available, severity, seriousness, relationship to study treatment, action taken, and outcome. A similar listing will be prepared for the pretreatment AEs.

Pretreatment AEs and TEAEs that lead to withdrawal from the study will be separately listed and summarized. Similarly, separate tabulations and listings will be prepared for pretreatment and treatment-emergent SAEs.

Descriptive statistics will be generated as appropriate (i.e., frequency for categorical data). Inferential statistical analysis comparing the AE data between active and placebo is not planned.

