5.2 Randomization

This is a single center, randomized, double-blind, 3-way crossover study. Approximately 30 eligible subjects will be randomized to placebo and 2 of the 3 possible dose groups: ORMD-0801 460 IU qd (in the evening), ORMD-0801 460 IU bid (in the morning and evening) and ORMD-0801 460 IU tid (morning, afternoon, and evening).

In order to estimate the morning, afternoon, and evening PD effect, each subject will have one period in which the PD blood samples are drawn in the morning, one period in which the PD blood samples are drawn in the afternoon and one period in which the PD blood samples are drawn in the evening. When the subject is on active therapy, the PD blood samples will be drawn after an active therapy dose (not after the placebo dummy). Thus, if the subject is taking ORMD-0801 460 IU qd, the PD blood samples will be drawn in the evening. If the subject is taking ORMD-0801 460 IU bid, the PD blood samples will be drawn in the morning or evening. If the subject is taking ORMD-0801 460 IU tid or placebo, the PD blood samples will be drawn in the morning, afternoon, or evening.

Integrium, LLC will generate and implement the randomization procedures for this trial. A computer-generated randomization schedule will be used for assigning treatment (active or placebo). The Investigational Site pharmacist will follow this randomization schedule to dispense the appropriate study treatment.

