2.3. Patient Disposition and Characteristics

An account of the patients by disposition will be tabulated overall. The number of patients included in each analysis population will be summarized. Patients not completing the study will be summarized and listed with the reason for their premature discontinuation. There will be an analysis of withdrawal rates by treatment group using both descriptive statistics and Fisher's exact test (2-sided and $\alpha=0.05$). A list of screening failures will also be provided.

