2.7.2. Hypoglycemic Events

The proportion (percentage) of patients affected by hypoglycemia and event rates for each of the classifications of hypoglycemic events will be reported by treatment received. The time-distribution of hypoglycemic episodes per patient will be reported for each treatment group.

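### The safety and disposition counting rules are written for parallel groups, so in this incomplete crossover they do not secure a fair comparison of each ORMD-0801 regimen with placebo.

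*Protocol*

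**What the plan says.** **Design.** Protocol 5.2: "Approximately 30 eligible subjects will be randomized to placebo and 2 of the 3 possible dose groups". Randomized dosing runs over Days 4 to 8 of each period. Single-blind placebo is given on Days 1 to 3 and Day 9 of every period (Protocol 5.3.1.1).

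**Safety population.** Protocol 8.4.1: "All randomized subjects who receive at least one dose of study treatment will be included in the safety analysis population". SAP 2.2 likewise defines a single overall set. Neither document defines a set per regimen.

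**TEAEs.** Protocol 8.4.2 tabulates TEAEs by treatment group, among other factors, and reports "the total number of subjects that experienced the TEAE, as well as the percentage of the population that this represents". When a subject has the same TEAE more than once, "the greatest severity and the worst-case attribution will be presented in the summary tables". In Protocol 8.4.2 and SAP 2.7.1 a TEAE is one that starts or worsens after the first randomized dose on Day 4, and no end is given. Protocol 7.2 and 8.4.2 also class AEs in the placebo run-in or placebo washout as pretreatment. No inferential comparison of AEs is planned.

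**Hypoglycaemia.** SAP 2.7.2 says that the percentage of patients affected and the event rates for each of the "classifications of hypoglycemic events will be reported by treatment received". It gives neither a time window nor a denominator.

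**Withdrawals.** SAP 2.3: "There will be an analysis of withdrawal rates by treatment group using both descriptive statistics" together with a two-sided Fisher's exact test at 0.05.

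**The concern.** Each rule would be routine if every subject received one treatment. Here one subject appears in three columns, and the columns have different sizes. The plan does not say who forms a column's denominator, which regimen owns an event that occurs between dosing blocks, or how a term reported under two regimens is graded in each column.

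Safety against placebo is a primary objective in Protocol 2.1 (Protocol 8.1 calls it a secondary endpoint), and hypoglycaemia is a secondary objective. With no AE inference planned, the descriptive percentages are themselves the safety comparison. A denominator that favours the active columns would therefore pass straight into the conclusions.

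**Working it through.** The plan gives no power or precision figure to reproduce. It states that "This study is not powered for statistical significance". The checks below are of exposure, timeline and the withdrawal test.

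**1. Denominator.** Inputs: 30 subjects, each with one placebo period and two active periods.

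- Subject-periods: 30 × 3 = 90, of which 30 are placebo and 60 active.
- Per active regimen, if the three possible pairs are equally used (an assumption; allocation sits in a separate randomization plan): 60/3 = 20.
- With pairs used 5, 10 and 15 times instead, the three regimens have 15, 20 and 25 subjects.

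Printed percentage = true percentage × (number exposed / 30):

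| Exposed | Factor | A true 20% prints as |
|---|---|---|
| 30 (placebo) | 1.00 | 20.0% |
| 25 | 0.83 | 16.7% |
| 20 | 0.67 | 13.3% |
| 15 | 0.50 | 10.0% |

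At equal risk, placebo 6/30 = 20.0% and active 4/20 = 20.0%, but the active column would show 4/30 = 13.3%. If 6 of 20 are affected on active (30%), the column shows 6/30 = 20%, the same as placebo. Under balance all active columns shrink by the same factor, so comparisons among them are undisturbed. Under imbalance they are disturbed too.

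**2. Repeat events.** Take a subject with a mild event on placebo and a severe event of the same term on an active regimen. The rule keeps the greatest severity per subject and does not add within regimen. Followed literally, the severe grade either appears in both columns or removes the placebo event. No size can be put on this from the documents.

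**3. Event window.** With 10-day periods and 14 days from Day 10 to the next Day 1, periods start on study days 1, 24 and 47. Period 3 Day 10 is day 56 and follow-up is day 63 to 65, which agrees with the Protocol's figure of about 65 days.

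- Literal TEAE window: day 4 to day 63–65, or 60 to 62 days.
- Randomized dosing days within it: 3 × 5 = 15, or 24% to 25%.
- Days that meet both the TEAE and the pretreatment definitions: the run-ins of Periods 2 and 3 (2 × 3 = 6) plus Day 9 of each period (3), which makes 9.
- Remaining days (Day 10s, between-period gaps, follow-up): 60 − 15 − 9 = 36 to 62 − 15 − 9 = 38.

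No rule assigns events on those 45 to 47 non-dosing days to a regimen. Hypoglycaemia by treatment received inherits the gap. An episode on Day 9 follows the last randomized dose, at about 10 pm on Day 8, but falls on a placebo day.

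**4. Withdrawal test.** Fisher's exact test requires independent groups. Here the columns draw on the same 30 subjects, each can withdraw only once, and a subject who leaves never enters the later columns. Even ignoring this, the test says little. For 4/20 against 0/30, p = C(20,4)/C(50,4) = 4845/230300 = 0.021, and this is the smallest active count that reaches 0.05 when no one withdraws on placebo. With 1/30 on placebo it takes 5/20 (p = 0.032), and with 2/30 it takes 6/20 (p = 0.047). Treating the columns as independent, the actual size is 0.0003, 0.005 and 0.018 at assumed withdrawal rates of 2%, 5% and 10% per period.

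**The case against.** Much can be said for the plan. AEs are tabulated by treatment group and hypoglycaemia by treatment received, so attribution to regimen was intended. The population in the percentage rule could mean the subjects treated in that column. SAP 2.7.1 does not repeat that phrase or the collapsing rule, and the table shells, held in a separate file, may give column denominators. Worst-grade collapsing is ordinarily done within a column, and all TEAEs are listed with dates and severity. Randomized dosing is planned as five days for every regimen. SAP 2.7.2 plans event rates and a time distribution, not proportions alone. The Fisher test touches disposition only.

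These points limit the conclusion but do not remove it. The prespecified text should not depend on an unseen shell, and a column denominator would not supply an event window or resolve the double definition.

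Two stronger readings are tempting. The first is that the regimen columns cannot be compared at all. The documents do not support this: once denominators and windows are stated, five planned days per regimen make the columns descriptively comparable.

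The second is that hypoglycaemia would set 17 placebo days (3 × 4 + 5) against 5 days per active regimen. At an assumed 2% daily risk this gives 1 − 0.98^17 = 29.1% affected against 1 − 0.98^5 = 9.6%. That pools run-in and Day 9 placebo into the placebo column. Protocol 7.2 and 8.4.2 class such events as pretreatment, Protocol 7.3.1 treats hypoglycaemia as an AE, and SAP 2.7.7 keeps run-in apart from end of treatment for CGM thresholds. It is a worst case that the text largely contradicts.

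**Conclusion.** The concern holds in this form: the written rules do not fit an incomplete crossover, and they leave the comparison of active with placebo unsecured. Read literally, the percentage rule understates active TEAE incidence by a factor of 0.67 against placebo. That figure rests on two conditions: that the denominator really is the single safety population, and that about 20 subjects receive each active regimen. For 15 to 25 exposed the factor is 0.50 to 0.83. It should not be reported as an established one-third understatement.

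The missing within-regimen collapsing, the open-ended TEAE window with its 9 doubly defined days per completer, and the absent hypoglycaemia window are gaps whose effect cannot be sized from the documents. The Fisher test is wrong for this design because its independence assumption fails. It is the least important part, since it does not affect the AE or hypoglycaemia columns.

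**What to change.** Amend Protocol 8.4.2 and SAP 2.3, 2.7.1 and 2.7.2, and align the table shells:

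- **Denominator.** For each regimen, use the subjects dosed in that regimen's period.
- **Repeat TEAEs.** Take greatest severity and worst attribution within subject and regimen.
- **Window.** Assign TEAEs and hypoglycaemia to the period's regimen over one common window, from the first randomized dose on Day 4 to a fixed time after that period's last randomized dose. State how later events are classed. Report run-in events separately in every period, and give rates per subject-day. Protocol 8.3 already sets an 8-hour cut-off after the last dose for CGM, so a rule of this kind is familiar to the plan. The length for AEs is the sponsor's choice.
- **Withdrawals.** Report counts descriptively by regimen and period over subject-periods started, and drop the Fisher test.

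The cost is wording and table programming, with no new data. Active-regimen percentages may look less favourable than under the literal rule, and one p-value is lost.

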8.4.3 Laboratory Evaluations

Individual clinical safety lab (hematology, serum chemistry, and urinalysis) values will be listed by visit and summarized using descriptive statistics as appropriate (i.e., mean, median, range, and standard deviation for continuous data and frequency for categorical data). Individual change from baseline (Screening) in laboratory values will be calculated and summarized descriptively. Shift tables from baseline (Visit 2/Day 1) to postdose (Visit 3) will also be produced for the laboratory assessments based on the categories of Low, Normal, and High. A clinically significant change from baseline (Screening) will be recorded as an AE if deemed appropriate by the Investigator.

8.4.4 Vital Signs

Individual vital sign measurements (height, weight, seated SBP/DBP, heart rate, and temperature) will be listed by measurement time and summarized using descriptive statistics as appropriate (i.e., mean, median, range, and standard deviation). Individual change from baseline (predose Day 1) in vital sign measurements will be calculated and summarized descriptively. A clinically significant change from baseline (predose Day 1) will be recorded as a TEAE if deemed appropriate by the Investigator.

8.4.5 12-lead ECG

Individual 12-lead ECG assessments will be listed by visit and summarized using descriptive statistics as appropriate (i.e., mean, median, range, and standard deviation for continuous data and frequency for categorical data).

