3.3 Visit 2 (Treatment Periods 1, 2, and 3)

3.3.1 Period 1

Subjects will report to the CRU on the morning of Day 1.

3.3.1.1 Day 1

- Review of medical history;
- Review of medications and supplements;
- Measurement of vital signs (weight, seated SBP/DPB, and heart rate);

- Provide the first dose of single-blind placebo at least 45 minutes prior to breakfast;
- Provide breakfast;
- Subjects will be fitted with the continuous glucose monitoring (CGM) device and data recording will begin;
- Provide 4 doses (8 capsules) of single-blind placebo and instruct subjects to take one dose at least 45 minutes before lunch, one dose at bedtime, one dose at least 45 minutes before breakfast on Day 2, and one dose at least 45 minutes before lunch on Day 2.
- Adverse events will be monitored and recorded.
- Subjects will be instructed to return to the CRU at approximately 5pm (± 30 minutes) on Day 2.

3.3.1.2 Day 2

- Admission to the CRU at approximately 5pm (± 30 minutes);
- Review of medications and supplements;
- Measurement of vital signs (weight, seated SBP/DPB, heart rate, and temperature);
- Perform breathalyzer;
- Collect a urine sample for:
 - Drug screen;
 - Pregnancy testing (WCBP only)
- Provide a standardized diabetic meal at approximately 7pm (± 60 minutes). Standardized meals will continue throughout the remainder of the study Period.
- Provide a dose of single-blind placebo at approximately 10pm (± 60 minutes).
- Continue CGM monitoring;
- Adverse events will be monitored and recorded.

3.3.1.3 Day 3

- Review of medications and supplements;
- Measurement of vital signs (weight, seated SBP/DPB, heart and rate);
- Provide a dose of single-blind placebo at approximately 7am (± 60 minutes);
- Provide breakfast no sooner than 45 minutes after the morning dose;
- Provide a dose of single-blind placebo at approximately 1pm (± 60 minutes), at least 45 minutes prior to lunch;
- Provide lunch no sooner than 45 minutes after the afternoon dose;

- Provide dinner at approximately 7pm (\pm 60 minutes);
- Provide a dose of single-blind placebo at approximately 10pm (\pm 60 minutes);
- Collect a blood sample according to schedule (per randomization scheme, either morning, afternoon, or evening) prior to the specified dose of placebo for:
 - Pre-dose PD analysis
 - Serum chemistry
- Collect scheduled (per randomization scheme) postdose PD blood draws every 30 minutes (\pm 5 minutes) until 5 hours has elapsed;

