6.3.2 Vital Signs

Vital signs (including seated SBP/DBP, and heart rate) will be recorded at all visits as described in Table 1. Temperature will be recorded at Visit 2/Day 2 only. Vital signs will be measured after the subject has been sitting for at least 5 minutes in a quiet environment and prior to any blood draw that occurs at the same time point. During Treatment Periods 1, 2, and 3, vital signs will be measured on Day 1, at admission on Day 2, immediately prior to morning dosing on Days 3-9, and on the morning of Day 10 prior to discharge. The recorded seated SBP/DBP value will be the mean of two measurements taken 2 minutes apart and always using the non-dominant arm.

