2.7.4. Vital Signs

Results, together with changes from baseline, will be described using summary statistics for each parameter for each day in which vital signs are collected. Changes from baseline will be compared between treatments using an ANOVA model.

A clinically significant change from baseline may be recorded as an AE, if deemed appropriate by the PI or sponsor.

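### Vital-sign change is measured from Day 1, before run-in and admission, although a Day 4 pre-dose value exists; the SAP names no baseline or test days, and the TEAE wording conflicts with the plan's own definition

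*Protocol*

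**What the plan says.** Protocol 8.4.4 fixes the baseline: "Individual change from baseline (predose Day 1) in vital sign measurements will be calculated and summarized descriptively". It does not say whether this is Day 1 of each period or of Period 1 only. It then gives the recording rule: "A clinically significant change from baseline (predose Day 1) will be recorded as a TEAE if deemed appropriate by the Investigator".

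The day-by-day schedule in Protocol 3.3 shows what follows the Day 1 reading. The dose that day belongs to the run-in: "Provide the first dose of single-blind placebo at least 45 minutes prior to breakfast". The subject goes home with further placebo doses and returns on Day 2: "Admission to the CRU at approximately 5pm". Randomised dosing starts on the morning of Day 4 (Protocol 3.6, footnotes to Table 1). Protocol 6.3.2 has vital signs taken "immediately prior to morning dosing on Days 3-9, and on the morning of Day 10 prior to discharge", so every period has an in-unit value just before its first randomised dose.

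SAP 2.7.4 plans summaries of results and changes for each collection day, and then: "Changes from baseline will be compared between treatments using an ANOVA model". It defines no baseline day and does not say which days the ANOVA covers. The ANOVA is in the SAP only; Protocol 8.4.4 plans descriptive statistics. On event recording, SAP 2.7.4 says that a significant change may be recorded as an AE.

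The general definition in Protocol 8.4.2 is: "TEAEs are defined as any AE that starts or increases in severity after the first randomized dose of study treatment". Protocol 7.2 and SAP 2.7.1 agree, and Protocol 7.2 and 8.4.2 class events in the placebo run-in or washout as pretreatment.

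**The concern.** A baseline for a treatment comparison normally sits as close as possible before the treatment starts. Here the earliest run-in value was chosen. Between it and the first randomised dose lie three days of single-blind placebo, a return home, admission, and the start of standardised meals. Any shift from these is carried into the change score on every later day.

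Three things are at stake. The comparison of each regimen with placebo may be less precise than the collected data allow. Some between-treatment tests may be run on days when that period's treatment has not been given, so that a significant result says nothing about it. And a change arising in run-in meets two incompatible rules for its label. Safety against placebo is a primary objective (Protocol 2.1, SAP 1.3.1), so these tables will be read.

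The choice also departs from the plan's practice elsewhere. CGM change is taken from the last qualifying days before dosing (Protocol 8.3, SAP 2.8.1), and PK/PD change from Day 3 (SAP 2.8.2).

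**Working it through.** The documents give no SD, correlation, effect size or alpha for vital signs, so there is no planned figure to reproduce. Three checks can be made.

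**1. Days before randomised dosing**
- Baseline is Day 1 and the first randomised dose is on the morning of Day 4: 4 − 1 = 3 days.
- Post-baseline days in a period are Days 2 to 10, which is 9 days. The Visit 3 reading is left out because it is not part of a treatment period.
- Days 2, 3 and 4 precede that period's first randomised dose, Day 4 because its reading is pre-dose: 3 of 9. Day 2 is also an evening reading, while the others are morning readings.
- If, and only if, one ANOVA is run per day for weight, SBP, DBP and heart rate, there are 9 × 4 = 36 tests per analysis, of which 3 × 4 = 12 fall on these days.
- If each were tested at 0.05 (assumed; the SAP gives 0.05 only for the withdrawal-rate test) and the tests were independent, the chance of at least one false positive per parameter over the three days is 1 − 0.95³ = 14.3%. The three changes share one Day 1 value, so they are likely to be positively correlated and the true figure lower, though not below 5%.
- With the Day 4 pre-dose value as baseline, none of the later days (5 to 10) precedes randomised dosing.

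**2. Noise in the change score**

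With equal variance σ² on both days and correlation r, Var(change) = 2σ²(1 − r).
- Assume r = 0.5 to 0.7 with Day 1 and 0.7 to 0.8 with Day 4. In units of σ², the variance is 1.0 to 0.6 from Day 1 and 0.6 to 0.4 from Day 4. The reduction runs from 0% (0.7 and 0.7: 0.6 to 0.6) to 60% (0.5 and 0.8: 1.0 to 0.4).
- Assume instead a correlation that decays with each day (AR(1), daily correlation ρ). The Day 8 change has variance 2σ²(1 − ρ⁷) from Day 1 and 2σ²(1 − ρ⁴) from Day 4:

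| ρ | From Day 1 | From Day 4 | Ratio |
|---|---|---|---|
| 0.5 | 1.984 | 1.875 | 1.06 |
| 0.7 | 1.835 | 1.520 | 1.21 |
| 0.9 | 1.043 | 0.688 | 1.52 |
| 0.95 | 0.603 | 0.371 | 1.63 |

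- If the correlation is the same at every lag, the ratio is 1.0 and nothing is gained.

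**3. Event label**

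Take a significant change first seen on Day 2 or Day 3.
- Protocol 8.4.4: a TEAE, if the investigator deems it appropriate to record it.
- Protocol 7.2 and 8.4.2: pretreatment, because it arose in the placebo run-in.
- SAP 2.7.4: an AE, with no statement on emergence.

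The investigator's discretion in 8.4.4 governs whether the change is recorded, not which label it carries. The neighbouring sections on laboratory values and physical examination (Protocol 8.4.3 and 8.4.6) both say AE; only 8.4.4 says TEAE.

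**The case against.** The best case for leaving the plan alone has four parts.

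First, every subject receives placebo on Days 1 to 3 and sequences are randomised, so the home-to-unit shift should be the same under each treatment. This stands. A reader might infer that the Day 1 baseline biases the comparison for or against the drug; the design does not support that.

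Second, the SAP attaches the by-day wording to the summaries, and its ANOVA sentence names no day. This stands too. The count of 12 in 36 tests is conditional, and it would be wrong to report it as what the SAP specifies. What remains is that the SAP leaves both the baseline and the tested days open.

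Third, the general definitions would keep most run-in events out of the treatment-emergent tables. This largely stands: a reader might infer that such events will be tabulated as treatment-emergent, but the documents show a conflict of wording, not a settled rule. The definitions do not remove it entirely. A drift that began in run-in may first be judged significant, against Day 1, only after Day 4.

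Fourth, vital signs carry limited weight. Protocol 8.1 calls safety a secondary endpoint judged mainly on adverse events, places vital signs among the secondary safety assessments, and says the study is not powered. A value before the run-in is also a coherent descriptive reference, and Day 1 is itself a morning visit to the unit. These points limit the importance but give no reason to prefer Day 1 for the treatment comparison when a later value before randomised dosing is already collected. SAP 1.2 reads as if subjects are housed from the start of run-in, but the detailed schedule in Protocol 3.3 places admission on Day 2.

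**Conclusion.** The point holds as a modest, inexpensive correction. The vital-sign baseline is three days earlier than it need be, and the SAP compares treatments on change from a baseline it does not define, over days it does not name. One sentence in Protocol 8.4.4 contradicts the TEAE definition used in the rest of the plan.

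The day count (3 of 9) and the wording conflict follow from the text alone. Treating those three days as tested assumes that the ANOVA follows the by-day summaries and takes its baseline from the Protocol. The precision gain cannot be fixed. Pairing the low ends and then the high ends of the assumed correlation ranges would suggest a tidy 40% or 33% reduction in variance, but the same ranges allow anything from 0% to 60%, and the documents supply nothing to narrow them. The harm is possible noise, uninformative tests and an inconsistent label.

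**What to change.** In Protocol 8.4.4 and SAP 2.7.4:
- Define baseline for weight, SBP, DBP and heart rate as the same period's Day 4 pre-dose value, the last before that period's randomised dosing. This also settles which period the baseline belongs to.
- Limit the between-treatment ANOVA to values taken after that dose, and name the days in the SAP.
- Keep the run-in days as descriptive summaries, outside the treatment comparison.
- In 8.4.4, replace TEAE by AE and refer to the 8.4.2 definition for classification.
- Leave temperature (Day 2 only, Protocol 6.3.2) and height (Screening only, Protocol 6.3.1) out of the change analysis, since neither has a change from baseline within a period.

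The cost is wording in two sections. The Day 4 value is already collected, so no procedure is added. The one loss is that change from the value before run-in is no longer the main summary.
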